6.1 Tumour characteristics

Pathology outcome	Number of patients (%)
HCC patients	
T-stage	
N-stage	
M-stage	
Histologic grade (G1-4)	
Resection (R0, R1, R2)	
Distance to nearest resection margin Median (range)	
Tumour necrosis (%) Median (range)	
Viable tumour (%) Median (range)	
Vascular changes	
Colorectal cancer patients	
Resection margins (R0, R1, R2)	
Grade (G1, G2, G3, G4)	
Tumour necrosis (%) Median (range)	
Viable tumour (%) Median (range)	
Vascular changes	

6.2. Tumour size/measurement

- The longest diameter of each lesion (mm) is measured at baseline and again on the day before surgical resection.
- The sum of the diameters can be taken for each patient, using the same lesions.
- Produce a waterfall plot showing the change in the sum from baseline to pre-surgery.
- Change in tumour size can also be compared using a paired t-test or Mann-Whitney test, depending on whether Normally distributed or not.
- Waterfall plot obtained for all patients, then separately for HCC and mCRC.

7. Concomitant Medications

Patient ID	Drug name/type	Time (days) from day of BTG treatment to start of non-trial drug
1	A	
1	B	
1	C	
2	D	
2	E	
2	F	

8. Follow up and deaths

	All patients	HCC	mCRC
	n (%)	n (%)	n (%)
No. patients who died			
Cause of death			
No. patients who dropped out/withdrew from the trial			
Reasons for withdrawal			
Lost to follow up			

9. Other Safety Parameters

Other safety parameters such as ECG, vital signs and physical examinations will be summarised

For laboratory parameters, observed values, changes from baseline, shifts in CTC grade and normal values/above and below normal values will be summarised with descriptive statistics. A listing of individual laboratory data will be provided with values outside normal ranges flagged.

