## **9. STATISTICAL CONSIDERATIONS**

### **9.1. Study Design and Determination of Sample Size**

The statistical analysis in this study will be primarily descriptive, to assess the safety and tolerability of the study treatment, as well as the distribution of the product following delivery. The study is not statistically powered. A staged enrollment will be performed, allowing for a safety

review after three patients have completed study treatment and follow up. Provided the safety committee deems that there is no significant toxicity related to BTG-002814, a further 9 patients will be enrolled in order to have a target sample size in the study of 6 patients with HCC and 6 patients with liver metastases from CRC. If up to two patients fail to complete study treatment and follow up, they will be replaced, giving a maximum total sample size of 14.

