VEROnA

A window of opportunity study of vandetanib-eluting radiopaque beads (BTG-002814) in patients with resectable liver malignancies

Protocol Number:	BTG-002814-01
------------------	---------------

STATISTICAL ANALYSIS PLAN

Date finalised	16 May 2019
Version number	1.0
Prepared by	[name], [name], [name]

Signed: [name]

Contents

1. Summary description of the trial
2. Baseline characteristics
3. Administration of BTG-002814
4. Primary endpoints (adverse events and plasma/tissue drug concentrations)
5. Secondary endpoints
6. Tumour pathology of the surgical resection
7. Additional treatments
8. Follow up and deaths

1. Summary description of the trial

Sample size	A target of 12 patients
Intervention arms (what treatments were given)	BTG-002814 (vandetanib-eluting radiopaque embolic beads), given 7-21 days before surgery.
Primary trial objectives	Primary objectives: 
• To assess the safety and tolerability of treatment with BTG-002814• Measure the plasma and resected liver tissue concentrations of vandetanib and the N-desmethyl metabolite following treatment with BTG-002814
Primary outcome measures	
• Adverse events (AEs) related to treatment with BTG-002814 using the standardised grading criteria (National Cancer Institute- Common Terminology Criteria for Adverse Events- Version 4.0 (NCI-CTCAE v4.0))• Concentration of vandetanib and N-desmethyl vandetanib in plasma and in resected liver tissue following treatment with BTG-002814.

[figure not shown]
SAP developed according to protocol version 6, 03 December 2018

The analyses will be performed using SAS (likely version 9.4).

Missing data in the analyses below will be indicated as such in tables (there will be no imputation).

Secondary objectives

 • Evaluate the anatomical distribution of BTG-002814 on non-contrast enhanced imaging using 4D CT • Evaluate histopathological features in the surgical specimen following treatment with BTG-002814 • Assess changes in blood flow on dynamic contrast-enhanced magnetic resonance imaging (DCE-MRI) following treatment with BTG-002814
Secondary outcomes measure

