4.2.2 Resected tissue

For each patient, provide a concentration-time plot for:

- vandetanib
- N-desmethyl metabolite

(concentration as the y-axis and time as the x-axis).

Each plot would be indicated as to whether the patient had HCC or mCRC.

This will be for:

- malignant tissue – three measurements for each patient:
 - Centre of tumour
 - Mid tumour
 - Edge of tumour
- non-malignant tissue
 - 1 cm from the edge of the tumour
- paired samples (difference, per patient, using malignant (based on the average of the 3 locations/samples) minus non-malignant values). Can be analysed using a t-test or non-parametric test
- Describe technical reasons for missing data points

5. Secondary objectives/outcomes (other blood, tissue and imaging markers)

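### SAP 6.2 pairs the paired t-test with Mann-Whitney, a test for independent samples, for within-patient change in tumour size

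*SAP*

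**What the plan says.** SAP 6.2 sets the measurement out clearly. Each lesion is measured twice: "The longest diameter of each lesion (mm) is measured at baseline and again on the day before surgical resection". The unit of analysis is one sum per patient: "The sum of the diameters can be taken for each patient, using the same lesions". The display is of change: "Produce a waterfall plot showing the change in the sum from baseline to pre-surgery". The test follows: "Change in tumour size can also be compared using a paired t-test or Mann-Whitney test, depending on whether Normally distributed or not".

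Normality is therefore the only switch between the two tests. The section does not say whether it is judged on the within-patient changes or on the sums, or whether change is in mm or percent.

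The only disease split in 6.2 concerns the plot: "Waterfall plot obtained for all patients, then separately for HCC and mCRC". SAP section 1 gives the size of the trial as "A target of 12 patients", and Protocol 9.1 states: "The study is not statistically powered".

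**The concern.** Mann-Whitney compares two independent samples. Used on baseline and pre-surgery sums from the same patients, it ignores who each sum belongs to and sets the treatment change against the whole spread of tumour size between patients. In 12 patients whose tumour burden differs widely, a consistent shrinkage can disappear in that spread.

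At stake is a misleading p-value in a small report. A waterfall plot with every bar pointing down could sit beside a clearly non-significant test, and a reader might take the test as evidence of no change. A programmer following the SAP literally would run it. The paired rank tests (Wilcoxon signed-rank, sign test) are named nowhere in the SAP.

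**Working it through.** The plan gives no power, alpha or sample-size figure for this analysis, so there is none to reproduce. The check has a structural part and an illustration of size.

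**Structure.** Same patients, same lesions, two times: paired. Paired t-test: paired. Mann-Whitney: not paired. The mismatch needs no calculation.

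**Why it is conservative.** Let *s* be the between-patient SD of log baseline sum and 0.12 the SD of within-patient log change. The difference in mean log sum has true variance 0.12²/n = 0.0144/n. A comparison that assumes independence works with (2*s*² + 0.0144)/n. The ratio of true to assumed variance is:

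- *s* = 0.3: 0.0144/0.1944 = 0.074
- *s* = 0.5: 0.0144/0.5144 = 0.028
- *s* = 0.7: 0.0144/0.9944 = 0.014

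This is the argument for means; the rank test behaves in the same way. The implied correlation, *s*/√(*s*² + 0.0144), is 0.93, 0.97 and 0.99.

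**Size.** From the documents: n = 12. Assumed, because the documents give no values: lognormal sums, the SDs above, true change −20%, two-sided 5%, and Shapiro-Wilk p < 0.05 on the mm differences as the Normality check. There were 4,000 simulated trials per setting, with exact critical values (Mann-Whitney U ≤ 37, signed-rank W ≤ 13). The largest simulation standard error is √(0.25/4000) = 0.8 percentage points.

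| | *s* = 0.3 | *s* = 0.5 | *s* = 0.7 |
|---|---|---|---|
| Mann-Whitney branch used | 10.6% | 28.8% | 46.4% |
| Power, SAP rule | 92.2% | 71.5% | 53.3% |
| Power, same rule with signed-rank | 100.0% | 100.0% | 99.6% |
| Power, Mann-Whitney alone | 29.8% | 2.6% | 0.4% |
| No true change: SAP rule rejects | 4.3% | 4.6% | 3.0% |

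The rows agree with each other. The t-test branch has power near 100%, so the rule's power should be about (1 − branch use) + branch use × Mann-Whitney power. For *s* = 0.3 that is 0.894 + 0.106 × 0.298 = 0.926. For *s* = 0.7 it is 0.536 + 0.464 × 0.004 = 0.538.

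**Sensitivity** (SAP rule against the rule with signed-rank; −20% and mm unless stated):

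- Change −10%: 66/55/39% against 72/70/66%.
- Change −5%: 23/13/14% against 25/18/22%.
- Normality judged on the sums: unpaired branch used in 23/38/54% of trials, rule power 86/64/46%.
- Normality and t-test on percent change: unpaired branch used in about 6-8%, rule power about 93-95% against 100%.
- Correlation only 0.5, *s* = 0.3: 60% against 63%.
- *s* = 0.2: 98.5% against 100%.

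**One data set.** Take invented baseline sums 18, 22, 27, 33, 38, 45, 52, 61, 74, 90, 112, 150 mm and shrink every patient by a random 16-25%, 1,000 times. The exact signed-rank p is 2/2¹² = 0.0005 each time, because all 12 changes have the same sign. The Mann-Whitney p never falls below 0.37. Shapiro-Wilk on the changes fails in about 35% of draws, and in those the SAP rule would report the Mann-Whitney result.

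**The case against.** Four points can be made for the plan.

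- *The size depends on inputs that are not in the documents, above all the scale.* Proportional shrinkage gives skewed mm differences when tumours vary in size, and that skew is what sends trials to the unpaired branch. On percent change most of the loss goes. This stands as a limit on the figures. Millimetres remain the natural reading, because 6.2 records diameters in mm and a paired t-test compares the two sums. A 20% change with small scatter also favours a large contrast; with weaker effects the absolute loss is smaller, as shown above.
- *Little depends on the test.* It is optional, tumour-size change is not a primary, secondary or exploratory endpoint, no decision rule uses it, and the waterfall plot shows the data directly. This stands and sets the severity.
- *It is probably a slip of name.* The paired partner and the insistence on the same lesions suggest that the authors understood the design. That is likely, but a named test is what gets programmed. Elsewhere the SAP leaves the choice open: section 4.2.2 says of the paired tissue samples "Can be analysed using a t-test or non-parametric test", and section 5.5 asks only for non-parametric tests on within-patient biomarker change. Only 6.2 names an unpaired test.
- *Mann-Whitney might be meant to compare change between HCC and mCRC.* The sentence does not support this. The choice turns on Normality, and a comparison between diseases would have an unpaired t-test as its parametric partner.

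**Conclusion.** The concern holds. As written, the non-Normal branch of SAP 6.2 applies an independent-samples test to paired data, and nothing elsewhere in the protocol or SAP corrects it. The error runs one way: for positively correlated pairs it hides real change and does not produce false positives. Under the stated assumptions on the mm scale, power at −20% falls from about 100% to between 92% and 53%, depending on how much tumour burden varies between patients. On percent change, or with low correlation or small spread, the loss is a few percentage points. Severity is minor, and neither co-primary endpoint is affected.

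**What to change.** In the last-but-one bullet of SAP 6.2, replace the Mann-Whitney test with the Wilcoxon signed-rank test on the within-patient change. State that Normality is judged on those within-patient changes, and say whether change is in mm or percent. If a comparison of change between HCC and mCRC is wanted, state it as a separate contrast, with Mann-Whitney or an unpaired t-test.

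The cost is one SAP sentence (two if the disease contrast is added). It needs no new data.
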